HRPP	Human Research Protections Program
Ig	Immunoglobulin
IRB	Institutional review board
LISB	Laboratory of Immune System Biology
MDCK	Madin Darby Canine Kidney
NCBI	National Center for Biotechnology Information
NIAID	National Institute of Allergy and Infectious Diseases
NIH	National Institutes of Health
PBMC	Peripheral blood mononuclear cell
PI	Principal investigator
RNA	Ribonucleic acid
RNA-seq	RNA sequencing
SAE	Serious adverse event
SARS-CoV-2	Severe acute respiratory syndrome coronavirus 2
SRA	Sequence Read Archive
TBNK	T, B, and natural killer (cells)
TDaP	Tetanus, diphtheria, and pertussis (vaccine)
UP	Unanticipated problem
USPHS	United States Public Health Service

Protocol Summary

- Short Title:** Immune response to flu vaccine
- Sample Size:** N=170 (n=24 subjects enrolled in year 1; targeting up to n=120 new subjects in year 2 and n=7 new subjects per year for years 3-5)
- Accrual Ceiling:** N=300
- Study Population:** Healthy volunteers aged 18 years and older (no upper age limit)
- Accrual Period:** 5 years (enrollment open August through February each year)
- Study Design:** This is an open-label, prospective, exploratory study to assess the baseline and post-vaccination immune responses of healthy volunteers to an approved seasonal influenza vaccine. Subjects will undergo baseline blood collections on day -7 and on day 0 before receiving the study vaccine. After vaccination, blood will be collected on days 1, 7, 14, 28, 70, and 100. Optionally, subjects may also give blood once a month, as requested, up until 1 year after vaccination. Research evaluations will include vaccine antibody titers. Additional evaluations may include peripheral immune cell phenotyping, RNA sequencing (RNA-seq) of whole blood and defined peripheral blood cell subsets, and measurement of serum proteins and antibodies. Subjects may optionally provide stool samples at some visits for exploratory microbiome assessments. Additionally, subjects may optionally continue study participation annually through the 2023-24 influenza season.
- Study Agent Description:** An approved inactivated seasonal influenza vaccine administered once by intramuscular injection. The study vaccine will be the vaccine stocked by the NIH pharmacy, either Flucelvax Quadrivalent or Fluvirin (Seqirus Inc.) for subjects under 65 years, or Fluzone High-Dose (Sanofi Pasteur) for subjects 65 years and older.

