3.1 Description of the Study Design

This is a prospective, open-label, exploratory study to evaluate the baseline immune state and post-vaccination immune responses of healthy volunteers to the seasonal influenza vaccine. The study vaccine is approved and indicated by the US Food and Drug Administration (FDA) for active immunization for the prevention of influenza disease caused by influenza virus subtypes A and B. Blood samples will be collected at various timepoints before and up to 100 days after vaccination to explore short- and long-term immunological effects of immunization. Blood may also be collected at optional monthly study visits up until 1 year after vaccination. Subjects may optionally provide stool samples on days -7, 0, 28, and 100.

Subjects will remain on study and may optionally repeat study visits (including vaccination) annually through the 2023-24 influenza season, with final study follow-up up to 1 year after vaccination. Sampling individual subjects across several influenza seasons will allow us to monitor for multi-season responses.

Blood will be evaluated to characterize immune response parameters, primarily changes in antibody titers following vaccination. These evaluations will be used to assess expected response to the vaccination in order to identify baseline and early response correlates of vaccination responses (e.g., by searching among the many parameters we will measure, as listed in section 7.2). Other important immune response parameters include the frequency of peripheral monocytes and interferon transcriptomic signatures (past studies suggest both can be detected in the blood on day 1 following influenza vaccination), as well as the frequency of plasmablast and certain CD4⁺ T-cell subsets (detectable around day 7 in past studies with influenza vaccination). In this study, these parameters should be captured exactly on days 1 and 7, as the earlier CHI study of influenza vaccination demonstrated that measuring these on the specified days will minimize variability and maximize detection of biologically important signals.³ Additional research evaluations may include flow cytometry and transcriptome and genetic analyses.

In year 2 of this protocol, enrollment will be enriched according to history of SARS-CoV-2 infection. We will enroll up to 120 subjects by consecutive sampling in the following cohorts:

- Up to n=40 subjects with no history of SARS-CoV-2 infection, as determined by a negative antibody test at screening.

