- Up to n=40 subjects with confirmed symptomatic SARS-CoV-2 infection, as determined by a documented positive polymerase chain reaction (PCR) test, and a positive antibody test at screening.
- Up to n=40 subjects with confirmed SARS-CoV-2 antibodies at screening or from an FDA-approved test as documented by the subject but with no history of symptoms.

This design will allow comparison between cohorts to explore the long-term immunological effects of SARS-CoV-2 infection. Recruitment in year 2 will be targeted toward these groups, and enrollment for each cohort will be stopped when its sample size is achieved for the year.

Because the vaccine response to the seasonal influenza vaccine in AA people has only started to be explored,¹⁰ we will recruit up to 10 AA subjects (of the 40) for each group described above in order to evaluate the relationship between AA race and vaccine responses in each of the three cohorts above.

Because obesity is associated with decreased vaccine responsiveness,¹¹ we will exclude individuals with a body mass index (BMI) ≥ 30 .

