15.2 Sample Size Justification

This is a hypothesis-generating study designed to examine relationships between different biomarkers measured at baseline and post-vaccination immune responses. To set the sample size, we used data from a previous study designed to examine biomarkers (09-H-0239).³ That study identified a significant relationship between $Y = \text{adjMFC}$ (a measure of vaccine-induced immune response adjusted for baseline response) and $X = \text{ID96_0}$ (a baseline readout of the frequency a $\text{CD38}^+ \text{CD20}^+$ memory B cell population). The estimated slope was 0.29 with an estimated standard error of $0.12 = \sqrt{\text{var}(R)/((n-1)*\text{var}(X))}$, where $\text{var}(R) = 2.09$ is the sample variance of the residuals from the regression line, $\text{var}(X) = 3.03$ is the sample variance of X , and $n = 49$ is the sample size of that study.

We used these estimates as a reference to set the sample size for the current study with the objective to identify a *new* biomarker that correlates with adjMFC with a similar or stronger relationship than was observed in 09-H-0239. We assumed the same error variance of $\text{var}(R) = 2.09$ and the same sample variance of $\text{var}(X) = 3.03$, and we assumed that the true slope is 0.29. We determined the power by using the Wald test where the slope is zero (i.e., the Wald test is $B/\text{se}(B)$ where B is the estimated slope and $\text{se}(B)$ is the estimated standard error). We assumed that this test is approximately standard normal under the null and approximately normal with mean $0.29/\sqrt{\text{var}(R)/((n-1)*\text{var}(X))}$ and variance 1 under the alternative.

We plan to correlate adjMFC with separate distinct collections of biomarkers (e.g., immune phenotyping as measured by flow cytometry or CyTOF, or RNA-seq). For each distinct collection, a multiplicity adjustment would be performed. Power calculations were performed (Table 2) considering various sample sizes, allowing for 5% missing data, and using a two-sided test with an alpha of 0.05 and with an illustrative Bonferroni adjustment for a moderate collection of biomarkers (50; e.g., nontrivial peripheral blood cell subsets measured by flow cytometry or CyTOF). With a sample size of 170 and 10% missing data, we have more than 80% power to identify biomarkers that have true slopes of 0.29 or better even with adjustment for 50 multiple comparisons.

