Table 2. Power to detect an association between a baseline biomarker and adjMFC under different sample sizes and multiplicity corrections.

Sample Size	Effective Sample Size (10% missing data)	Power with Adjustment for 50 Comparisons
120	108	.63
170	153	.85
230	207	.96

Sample Size	Effective Sample Size (10% missing data)	Power with Adjustment for 50 Comparisons
280	252	.99

Subjects will have the option to participate for multiple years. Generalized estimating equations (GEE) analyses that use all available measurements from each subject with proper correction for within subject correlation will have greater power than those described in Table 2. Analyses will be stratified by year by including a separate term for each cohort year in the GEE models. Such stratification has a negligible effect on power calculations.

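### The stated N of 170 is 5 more than the yearly targets supply (165), and section 15.2 gives 5% missing data for a power table that uses 10%

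*Combined protocol and SAP*

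**What the plan says.** **Sample size.** The Protocol Summary gives "N=170 (n=24 subjects enrolled in year 1; targeting up to n=120 new subjects in year 2 and n=7 new subjects per year" for years 3 to 5. Section 3.1 repeats the year 2 limit: "We will enroll up to 120 subjects by consecutive sampling in the following cohorts". It lists three cohorts of up to 40 and adds that "enrollment for each cohort will be stopped when its sample size is achieved for the year". The Protocol Summary also gives a separate accrual ceiling of 300. Section 12.9 allows replacement of subjects who leave before day 14 of their first year, without giving a number.

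**Missing data.** Section 15.2 introduces the power table with "Power calculations were performed (Table 2) considering various sample sizes, allowing for 5% missing data". The next sentence reads "With a sample size of 170 and 10% missing data, we have more than 80% power", and the second column of Table 2 is headed "Effective Sample Size (10% missing data").

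**Multiplicity.** Section 15.2 says "We plan to correlate adjMFC with separate distinct collections of biomarkers" and then "For each distinct collection, a multiplicity adjustment would be performed". Section 15.3 says the adjustment controls the overall type I error rate at 0.05.

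**The concern.** N and power are the stated grounds for the size of the study. A reader who adds up the yearly targets gets a smaller number than the one the power statement uses. The shortfall cannot come from year 2, because each cohort there closes when full. A reader who takes the 5% at face value will also be unable to reproduce Table 2. What is at stake is whether the power claim holds once the figures are made consistent, and which figures belong in the protocol.

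**Working it through.** **Inputs, all from section 15.2:** slope 0.29, var(R) = 2.09, var(X) = 3.03, two-sided alpha 0.05, Bonferroni for 50 tests (0.001 per test, critical value z = 3.2905). The effective size is n = N × (1 − missing fraction).

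**Formula (the plan's Wald test):** power = Φ(μ − z), with μ = 0.29 / √(2.09 / ((n − 1) × 3.03)). The opposite tail is negligible.

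**Check on the reference study.** At n = 49 the standard error is √(2.09 / (48 × 3.03)) = 0.1199, against the stated 0.12.

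**Step 1: reproduce Table 2 and test the missing-data figure.**

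| N | n at 10% | Power at 10% | n at 5% | Power at 5% | Printed |
|---|---|---|---|---|---|
| 120 | 108 | .626 | 114 | .663 | .63 |
| 170 | 153 | .845 | 161.5 | .871 | .85 |
| 230 | 207 | .957 | 218.5 | .969 | .96 |
| 280 | 252 | .988 | 266 | .992 | .99 |

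For N = 170 at 10%: μ = 0.29 × √(152 × 3.03 / 2.09) = 4.305, and Φ(4.305 − 3.2905) = .8448. Strictly this rounds to .84, and the printed .85 appears if n replaces n − 1 in the formula (.848). The difference is well under one percentage point, whereas 5% missing would give .87. The first two rows separate the two assumptions clearly; the last row cannot. The printed effective sizes 108, 153, 207 and 252 are exactly 90% of N. Table 2 was therefore computed with 10%.

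**Step 2: add up the accrual.** 24 + 120 + 3 × 7 = 165, and 170 − 165 = 5. With years 1 and 2 as stated, years 3 to 5 would have to supply 170 − 24 − 120 = 26 rather than 21. That is 26 / 3 = 8.67 per year, so no whole-number yearly target gives exactly 170.

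**Step 3: power at 165.** With 10% missing, n = 148.5 and μ = 0.29 × √(147.5 × 3.03 / 2.09) = 4.241, so power = Φ(4.241 − 3.2905) = .829. Rounding n to 148 or 149 gives .827 or .831.

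**Step 4: margin.** An effective size of 142 is the smallest that gives 80% power. With 10% missing this means N = 158 (142 / 0.9 = 157.8, rounded up), which is below 165.

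**The case against.** The strongest reply is that neither point changes anything of substance. Power at 165 is still above 80%. The missing-data slip is corrected by the very next sentence, which uses the more conservative figure. The yearly numbers are targets, the accrual ceiling is 300 and early withdrawals are replaced, so enrolment is not limited to 165. The figure of 170 may simply be a planning value taken from a row of Table 2.

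Most of this stands, and it is why the point is minor. It does not explain the gap. The breakdown is given as the composition of 170 and misses its own total. The ceiling is a separate line, and the replacement rule has no number and is not tied to N.

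A reader might infer two stronger things that the documents do not support:

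- *That the study is underpowered.* Steps 3 and 4 show otherwise for the plan's 50-comparison case.
- *That sections 15.2 and 15.3 contradict each other on multiplicity, so that error across several biomarker collections is uncontrolled or power falls below 80%.* Section 15.2 sets the adjustment for each distinct collection, and its worked example applies 0.05 to a single collection of 50. Read that way, *overall* in 15.3 means across the tests in a collection and conflicts with nothing. The number of collections is not given and the 50 is called illustrative, so any error rate or power across collections would rest on outside assumptions. What remains is one undefined word.

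**Conclusion.** The point holds as two inconsistencies in the sample size justification, both minor. The stated N exceeds the itemised targets by 5, and the documents do not show which figure is wrong. If 165 is right, power for one collection of 50 biomarkers is .83 instead of the printed .85. The 5% in section 15.2 does not match the table it describes; 10% does. The conclusion of more than 80% power is unaffected.

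These results take the plan's slope, variances, normal approximation and 50-test Bonferroni adjustment as given. They leave out any gain from repeat-season data in the GEE analysis, which section 15.2 asserts but does not quantify.

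**What to change.** 1. **Protocol Summary and section 15.2.** Restate N as 165, with power .83 at 10% missing data, and add that row to Table 2. If 170 is the intended figure, correct the yearly targets so that they sum to it (26 across years 3 to 5, if years 1 and 2 stand) or say what the other 5 subjects are.
2. **Section 15.2.** Change 5% to 10% in the sentence introducing Table 2.
3. **Optional clarification in section 15.3, not the correction of an error.** Say that the overall rate of 0.05 applies within each distinct collection of biomarkers, as section 15.2 implies.

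The cost is wording only. There are no new procedures, and no additional subjects unless the yearly targets are raised by 5 in total, which the accrual ceiling of 300 allows. Restating N as 165 lowers the stated power by about two percentage points.

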15.3 Description of the Analyses

The primary analysis will be to correlate multiple baseline biomarkers with the vaccine-induced outcome adjMFC using GEE to reflect clustering at the subject level due to multiple measurements over multiple years. Analyses will be stratified by year by including a separate term for each cohort year in the GEE models. Two-sided testing will be performed with an adjustment for multiplicity such as the Bonferroni to control the overall type I error rate at 0.05.

For the first secondary analysis, a similar analysis strategy will be used as in the primary analysis, but the relationship between the vaccine-induced outcome adjMFC and baseline biomarkers (specifically ID_96 [CD38⁺ CD20⁺ B cell frequencies and/or transcriptomic signatures]) and post-vaccination biomarkers (specifically ID_87 [plasmablast cell frequencies and/or transcriptomic signatures]) will be examined separately. Specifically, we will evaluate 1) whether the slope between adjMFC and ID96_0 (measured at day 0) is zero using GEE, as described for the primary analysis with no adjustment for multiplicity, and 2) whether the slope between adjMFC and ID_87, measured at day 7/day 0) is zero using GEE, as described for the primary analysis with no adjustment for multiplicity. Both analyses are designed to replicate findings from 09-H-0239.³

Analysis of the secondary endpoint on SARS-CoV-2 will involve comparing the results of the above analyses by cohort: 1) those subjects with prior symptomatic SARS-CoV-2 infection, 2) those subjects with prior asymptomatic SARS-CoV-2 infection, and 3) those subjects without a history of SARS-CoV-2 infection.

The exploratory analyses will involve both unsupervised and supervised analyses using the framework developed in 09-H-0239. In addition to that framework, under this protocol we will be able to characterize immune responses and biomarker relationships over multiple seasons in the same individual. The first general aim is to perform unsupervised analysis of the immune states of the baseline along the measured phenotypic dimensions, including PBMC/cell subset

transcriptomes (genes and gene module activities), cell subset frequencies, and relative levels of circulating protein markers. In addition, using data from multiple baseline timepoints (for example, day 28 and beyond might be useful as additional baselines based on comparison to pre-vaccination timepoints to assess the extent of change), we can perform analyses to assess the inter-subject variability and temporal stability of parameters as was done in our earlier study. The parameters that are highly variable among but stable within subjects are good candidates for downstream prediction analysis and correlate discovery.

In addition to unsupervised analyses, specific markers known to be associated with vaccination responses will be assessed including, but not limited to, monocyte frequencies and interferon transcriptomic signatures on day 1, as well as B cell/plasmablast response on day 7.

We will use the same Monte Carlo cross-validation framework from 09-H-0239 to build predictive models and assess immune response correlates by first focusing on antibody titer response as the endpoint. The goal is to link baseline and early response status to antibody response. We will also use variable selection and multiple regression approaches, including Lasso, Ridge regression, and Elastic Net. Variable and model selections will be conducted through cross-validation.

We also plan to include unsupervised analysis without focusing on specific endpoints such as titers (e.g., by assessing the correlation between the most variable baseline states to the most variable response profiles among subjects).

16 Ethics/Protection of Human Subjects

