2.1 Primary Objective

Identify baseline correlates of immune response to the seasonal influenza vaccine in healthy individuals

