3.2 Study Endpoints

3.2.1 Primary endpoint

Change in antibody titer response to vaccination, as measured by microneutralization titers at day 0 and day 70 and its relationship with novel baseline biomarkers.

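### The primary endpoint concerns novel biomarkers, but the primary test cannot tell a marker that adds to the established CD38+ CD20+ population from one that only tracks it

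*Combined protocol and SAP*

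**What the plan says.** Section 3.2.1 defines the primary endpoint as the change in titer, "as measured by microneutralization titers at day 0 and day 70 and its relationship with novel baseline biomarkers". Section 3.2.2 puts the established baseline marker, CD38+ CD20+ B cell frequencies and/or transcriptomic signatures, into a secondary endpoint. Section 15.2 sets the sample size to find a new "biomarker that correlates with adjMFC with a similar or stronger relationship than was observed in 09-H-0239".

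On the analysis, section 15.3 says: "The primary analysis will be to correlate multiple baseline biomarkers with the vaccine-induced outcome adjMFC using GEE to reflect clustering at the subject level". It adds a term for each cohort year and a multiplicity adjustment such as Bonferroni. No term for ID96_0 is named; ID96_0 has its own test in the first secondary analysis. The power model in section 15.2 is a Wald test of zero slope for a single marker. The text does not say outright that one model is fitted per marker. That is inferred from the power model and the multiplicity adjustment.

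Section 15.3 also plans Lasso, Ridge and Elastic Net regression, as exploratory work. No section defines novel, or says that a marker must add anything to ID96_0.

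**The concern.** The candidate collections in section 15.2 are immune phenotyping by flow cytometry or CyTOF, and RNA-seq. The illustrative panel of 50 is "nontrivial peripheral blood cell subsets measured by flow cytometry or CyTOF". These are the same kinds of measurement that define the established marker, so some candidates may correlate with it.

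If ID96_0 is related to adjMFC, any such candidate has a nonzero marginal slope even when it has no effect of its own. A multiplicity adjustment does not screen it out, because its marginal null hypothesis is false. A significant primary result would then show that the marker is a baseline correlate. It would not show whether the marker is news or a restatement of the result from 09-H-0239. At stake is how the primary endpoint's word novel is to be read in the report.

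**Working it through.** **Inputs from section 15.2 and Table 2.** Slope 0.29, var(R) = 2.09, var(X) = 3.03, prior n = 49. Two-sided 0.05 with Bonferroni for 50 markers gives 0.05/50 = 0.001 per marker, critical value 3.2905. N = 170 with 10% missing gives n = 153.

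**Assumptions not in the documents.** The correlation ρ between a candidate and ID96_0, and the size of the ID96_0 effect in this study.

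**1. Reproduce the plan's figures.** Prior standard error: sqrt(2.09/(48 × 3.03)) = 0.1199 (stated 0.12). At n = 153 the standard error is sqrt(2.09/(152 × 3.03)) = 0.06736, the Wald mean is 0.29/0.06736 = 4.305, and power is Φ(4.305 − 3.2905) = 0.845 (stated .85). The other rows give 0.626, 0.957 and 0.988 (stated .63, .96, .99). The power model is therefore read correctly.

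**2. Chance that a pure proxy passes the primary test.** Take a candidate scaled to variance 3.03, with correlation ρ to ID96_0 and no effect of its own.

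- Marginal slope: 0.29ρ.
- Residual variance: 2.09 + 0.29² × 3.03 × (1 − ρ²) = 2.09 + 0.2548(1 − ρ²).
- Wald mean: m = 0.29ρ / sqrt(residual variance/(152 × 3.03)).
- Pass probability: Φ(m − 3.2905); the other tail is negligible.

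The last column halves the ID96_0 slope to 0.145 and keeps the total variance at 2.09 + 0.2548 = 2.3448. For example, at ρ = 0.9 the slope is 0.1305, the residual variance 2.2932, m = 1.849, and Φ(−1.441) = 0.075.

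| ρ | slope | residual variance | m | pass probability | at half slope |
|---|---|---|---|---|---|
| 0.5 | 0.145 | 2.281 | 2.060 | 0.109 | 0.012 |
| 0.7 | 0.203 | 2.220 | 2.924 | 0.357 | 0.032 |
| 0.8 | 0.232 | 2.182 | 3.371 | 0.532 | 0.049 |
| 0.9 | 0.261 | 2.138 | 3.830 | 0.705 | 0.075 |

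At slope 0.29 the probability reaches one half at ρ of about 0.78 and 0.80 only at about 0.96. OLS simulation at n = 153 agrees (0.12, 0.37, 0.53, 0.70).

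Other settings move the figure both ways, for ρ = 0.5, 0.7 and 0.8:

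- At effective n = 252 one proxy passes with 0.26, 0.68 and 0.85.
- With Bonferroni for 1000 markers at n = 153, one proxy passes with 0.02, 0.13 and 0.25.
- With five proxies in a panel (independent noise, simulated), at least one passes with 0.39, 0.73 and 0.80.

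All of this uses one record per subject. Repeat-year data would raise the pass rates.

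**3. What adjusting for ID96_0 does.** The adjusted slope of a pure proxy is zero. In simulation, the chance that it passes the marginal test and then has an adjusted slope significant at two-sided 0.05 is about 0.02 to 0.04 for ρ from 0.5 to 0.9.

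The price is precision: the standard error grows by 1/sqrt(1 − ρ²), which is 1.15, 1.40, 1.67 and 2.29 at ρ = 0.5, 0.7, 0.8 and 0.9. For a marker with its own slope of 0.29 given ID96_0, the chance that the adjusted 95% CI excludes zero is about Φ(4.305 × sqrt(1 − ρ²) − 1.96) = 0.96, 0.87, 0.73 and 0.47.

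**4. Measurement error in ID96_0.** Assume reliability 0.8. The adjusted slope of a pure proxy is then 0.29 × 0.25ρ/(1.25 − ρ²), or 0.036, 0.067 and 0.148 at ρ = 0.5, 0.7 and 0.9. Tested at 0.001, the adjusted slope of such a proxy is significant with probability 0.003, 0.008 and 0.024; at 0.05 the rate would be higher.

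**The case against.** The primary objective in section 2.1 is only to "Identify baseline correlates of immune response to the seasonal influenza vaccine in healthy individuals". A marker that shares variance with ID96_0 is still a baseline correlate, so the marginal test answers that objective. Where section 15.2 uses the word new, its criterion is itself a marginal correlation with adjMFC. The study is called hypothesis-generating, and no section makes significance an automatic declaration of novelty. All of this stands. The gap is confined to novel in the endpoint and new in the sizing objective.

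Three stronger readings are tempting, and the documents do not support them.

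- **Inflated type I error.** A reader might set the pass probabilities against 0.001. The hypothesis tested is a zero marginal slope, which is false for a proxy. These figures are power for a real correlation.
- **Proxies will probably be reported as novel.** The documents give no ρ. Overlap of gates does not fix how cell frequencies correlate across subjects, and one proxy at moderate ρ passes less than half the time.
- **The plan takes the ID96_0 effect as given.** The sizing text says "and we assumed that the true slope is 0.29", but of a new biomarker. Whether ID96_0 has an effect here is left to the first secondary analysis, and the prior estimate is imprecise (0.29, standard error 0.12, n = 49).

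It can also be said that the penalized regressions handle redundancy among markers. They do so in part, but they are exploratory and not tied to any statement about novelty. Finally, section 15.3 already counts transcriptomic signatures with the established CD38+ CD20+ marker, so some transcript proxies may fall outside novel from the start.

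**Conclusion.** The point holds as a gap between the primary endpoint and the primary analysis. The plan separates novel from established markers, but its primary test, as powered, contains nothing that could make that separation. The marginal test remains valid for finding baseline correlates, and its error control is not in question.

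The size depends on two unknowns. With an ID96_0 slope of 0.29, a pure proxy passes with probability 0.11 to 0.70 for ρ from 0.5 to 0.9. With half that slope it is about 0.01 to 0.08. The problem is therefore material if the 09-H-0239 association holds at its estimated size and the panel contains close relatives of ID96_0, and small if the 09-H-0239 estimate was too large. The remedy uses data already planned, so it is worth making in either case.

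**What to change.** In section 15.3, keep the marginal, multiplicity-adjusted test as the analysis for the objective of baseline correlates. For each marker that passes, add a refit of the same GEE with day 0 ID96_0, and any other established baseline signature that was measured, as covariates. Report the adjusted slope with its 95% CI and the marker's correlation with ID96_0. Describe a marker as adding to the established one only where the adjusted slope supports that; otherwise report it as a correlate not distinguished from ID96_0. Say in one sentence that this is how novel in section 3.2.1 is to be read.

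A hard significance gate on the word novel is not advised. At ρ = 0.9 it would drop about half of the markers with a full effect of their own.

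The cost is SAP wording and one further fit for each passing marker, with no new samples and no change in sample size. The drawbacks are loss of precision for markers strongly collinear with ID96_0, and some residual leakage of proxies if ID96_0 is measured with error. Both should be acknowledged when the adjusted slopes are interpreted.

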2.2 Secondary Objectives

- Validate the findings of prior study 09-H-0239, specifically the relationship between cell populations and/or gene transcripts at baseline and after vaccination that correlate with vaccine immune response
- Evaluate the effect of prior SARS-CoV-2 infection on the antibody response to the seasonal influenza vaccine in healthy volunteers

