3.2.2 Secondary endpoints

- Change in antibody titer response to vaccination, as measured by microneutralization titers at day 0 and day 70 and its relationship with established baseline biomarkers (CD38⁺ CD20⁺ B cell frequencies and/or transcriptomic signatures) and post-vaccination biomarkers (plasmablast cell frequencies and/or transcriptomic signatures)
- Difference in antibody titer response to vaccination between subjects with a history of symptomatic or asymptomatic SARS-CoV-2 infection and those with no evidence of SARS-CoV-2 infection

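### For the SARS-CoV-2 secondary endpoint, section 15.3 states only a by-cohort comparison of biomarker associations; no direct contrast of antibody response between cohorts is stated

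*Combined protocol and SAP*

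**What the plan says.** The objective in section 2.2 is: "Evaluate the effect of prior SARS-CoV-2 infection on the antibody response to the seasonal influenza vaccine in healthy volunteers". Section 3.2.2 turns it into an endpoint: "Difference in antibody titer response to vaccination between subjects with a history of symptomatic or asymptomatic SARS-CoV-2 infection and those with no evidence" of infection. Both concern the level of response in one group against another.

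Section 15.3 gives this endpoint one sentence: "Analysis of the secondary endpoint on SARS-CoV-2 will involve comparing the results of the above analyses by cohort". It then lists three cohorts: symptomatic infection, asymptomatic infection and no history of infection.

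Three analyses stand above that sentence:

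- The primary analysis: "The primary analysis will be to correlate multiple baseline biomarkers with the vaccine-induced outcome adjMFC using GEE".
- The first replication test: "whether the slope between adjMFC and ID96_0 (measured at day 0) is zero using GEE".
- The second replication test, which asks the same of the slope on ID_87 (day 7 relative to day 0).

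The only additional model term named is for season: "including a separate term for each cohort year in the GEE models". The outcome adjMFC is described in section 15.2 as "a measure of vaccine-induced immune response adjusted for baseline response".

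**The concern.** The endpoint is a difference in mean response between groups. The assigned analysis compares associations between groups. These are different quantities: the first is a cohort main effect, the second a biomarker-by-cohort interaction. Prior infection could lower the response of every subject by the same amount and leave each biomarker slope as it was. It could equally alter a slope and leave the mean response unchanged.

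If the section were carried out exactly as worded, the report would say whether biomarker associations differ by cohort. It would contain no named estimate, interval or test for the effect of infection on the response. Year 2 recruitment is built around this question, with up to 120 of the planned 170 subjects in the three cohorts (sections 3.1 and 15.2). Leaving the contrast unwritten also leaves its form (pooled or pairwise, adjusted or not) to be chosen after the data are seen.

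**Working it through.** **Inputs.** From section 15.2: var(R) = 2.09 (residual variance), var(X) = 3.03, slope 0.29, and the 10% missing data used in Table 2. From section 3.1: up to 40 subjects per cohort. With full cohorts and 10% missing, 36 remain per cohort, so 72 infected and 36 uninfected.

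**The plan's own figure.** Table 2 gives power 0.85 at N = 170 (153 effective) with Bonferroni adjustment for 50 tests. SE = √(2.09/(152 × 3.03)) = 0.0674; 0.29/0.0674 = 4.305; 4.305 − 3.291 = 1.015; power 0.845. The stated figure reproduces. It concerns a biomarker slope. The documents give no power or effect size for the SARS-CoV-2 endpoint, so what follows is illustrative.

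**Why slopes do not carry the endpoint.** Within a cohort, slope = Sxy/Sxx, computed from deviations about the cohort means. Adding a constant to every adjMFC value in that cohort changes neither Sxy nor Sxx, so the slope is unchanged. The same holds for a correlation. A test of equal slopes therefore rejects at its nominal 5% under a constant shift of any size.

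A simulation of 4,000 runs bears this out, with 40 versus 40, equal slopes of 0.29 and a shift of 1.0 unit:

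| Comparison | Average estimate | Rejection rate |
|---|---|---|
| Slope difference | 0.00 | 4.3% |
| Mean difference | 1.01 | 82.6% |

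**Direct contrast, 72 versus 36.** An unadjusted contrast uses the marginal SD of adjMFC: √(2.09 + 0.29² × 3.03) = √2.345 = 1.53. The smaller value √2.09 = 1.45 is the SD left after regression on ID96_0, so it does not apply here.

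- Standard error in SD units: √(1/72 + 1/36) = 0.204.
- Difference with 80% power, two-sided 0.05: (1.960 + 0.842) × 0.204 = 0.57 SD; × 1.53 = 0.88 adjMFC units.
- 95% CI half-width: 1.960 × 0.204 = 0.40 SD; × 1.53 = 0.61 units.

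**Slope comparison, 72 versus 36.** SE = √(2.09/(71 × 3.03) + 2.09/(35 × 3.03)) = √(0.00972 + 0.01971) = 0.172. For a slope difference of 0.29: 0.29/0.1715 − 1.960 = −0.269, so power is 39%. This comparison has limited power even for its own target.

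**The case against.** The strongest reply is that the sentence says what the analysis will involve, not all that it will contain. Section 3.2.2 already names the contrast, adjMFC is the outcome in every analysis listed, and section 3.1 says the design permits comparison of cohorts. A report of adjMFC by cohort would be compatible with all of this. That stands. A reader might infer that the plan excludes a direct contrast or could not produce one, and the documents do not support that. What remains is that no cohort term, contrast, test or interval for the endpoint is written down, and that the one analysis that is written down addresses something else.

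It may also be said that separate fits by cohort yield intercepts. An intercept is the expected adjMFC at a biomarker value of zero. It differs from one biomarker to the next, and the plan does not name it as the estimate.

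Section 15.2 calls the study hypothesis-generating, and section 1.2 says that comparing groups of volunteers is not its goal. This limits the weight of the point. But the section 1.2 statement sits uneasily with sections 2.2, 3.1 and 3.2.2, which set up exactly such a comparison, so it does not remove the gap.

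On the comparator, section 6.1 places subjects with a positive PCR and two negative antibody tests in the no-history cohort, while section 3.2.2 speaks of no evidence of infection. A reader might infer that the uninfected group is materially contaminated. The documents do not support that either: section 3.1 defines the cohort by a negative antibody test, and the number of such subjects is unknown. It is a separate question of classification that merits at most a sensitivity analysis.

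**Conclusion.** The concern holds in a limited form. The only analysis assigned to the SARS-CoV-2 endpoint targets effect modification of biomarker associations, whereas the endpoint is a difference in response. This is more than missing detail, because the stated analysis is insensitive by construction to a uniform effect of infection.

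The planned cohorts could support the direct contrast with 80% power for about 0.88 adjMFC units (0.57 SD) and a 95% CI of about ±0.61 units. These figures assume that the variances from 09-H-0239 carry over, that all three cohorts fill, that 10% of data are missing and that no covariates are used. The SD after adjustment for age and product cannot be derived from the documents.

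The issue is confined to one secondary endpoint of an exploratory study. All the data needed are collected in any case, and the primary analysis and Table 2 are unaffected. It should be fixed before analysis.

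**What to change.** In section 15.3, replace the sentence on this endpoint with the following:

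- State that adjMFC is the measure of antibody titer response for this endpoint; section 15.2 describes it only in general terms.
- Regress adjMFC on the three-level SARS-CoV-2 cohort, adjusted for age and for vaccine product (under 65 versus 65 and older). The cohorts are not randomised, and section 5.3.1 changes the product at 65, a step that a single age term does not capture.
- If repeat seasons are included, fit the model by GEE with the year term already planned, consistent with section 15.2: "Generalized estimating equations (GEE) analyses that use all available measurements from each subject".
- Main contrast: symptomatic plus asymptomatic infection versus none, with a 95% CI. Supportive: each infected cohort versus none, each with a 95% CI.
- Keep the by-cohort comparison of biomarker associations as exploratory.
- Optionally, repeat the main contrast without the PCR-positive, twice antibody-negative subjects in the uninfected group.

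Reconcile the statement of goals in section 1.2 with the cohort comparison in sections 2.2, 3.1 and 3.2.2.

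The cost is wording, one added regression and, if wanted, one sensitivity run. No new subjects, visits or assays are needed.
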